Aim 1: Examine the association between exposure to “natural” or “organic” cigarette descriptors and: 1) health risk expectancies (e.g., chemical content); 2) subjective effects of smoking (e.g., chemical taste); 3) smoking topography (e.g., total puff volume); and 4) biomarkers of exposure (e.g., salivary aldehydes).

H_{1.1}: More participants will rate cigarettes in the “natural” and “organic” conditions as having fewer chemicals relative to cigarettes in the “conventional” condition.

H_{1.2}: Participants’ average ratings of the “chemical aftertaste” of the cigarettes in the “natural” and “organic” conditions will be higher (e.g., closer towards the “less chemical aftertaste” side of the scale) relative to their average ratings of the cigarette in the “conventional” condition.

H_{1.3}: Total puff volume will be higher in the “natural” and “organic” conditions than the “conventional” condition.

H_{1.4}: Change in salivary aldehyde concentrations pre/post administration of the study cigarette(s) will be higher in the “natural” and “organic” conditions than the “conventional” condition.

Aim 2: Examine whether the relationships in Aim 1 differ by preference for a “natural/organic” cigarette brand (NAS smokers vs. non-NAS smokers).

H_{2.1}: Compared to non-NAS smokers, more NAS smokers will rate the “natural” and “organic” conditions as having fewer chemicals relative to their ratings in the “conventional” condition, but not relative to their own brand condition.

H_{2.2}: Compared to non-NAS smokers, NAS smokers’ average ratings of the “chemical aftertaste” of the cigarettes in the “natural” and “organic” conditions will be higher (e.g., closer towards the “less chemical aftertaste” side of the scale) relative to their average ratings of the cigarette in the “conventional” condition, but not relative to their own brand condition

H_{2.3}: NAS smokers’ total puff volume will be lower in the “conventional” condition than the “natural,” “organic,” and own brand conditions.

H_{2.4}: NAS smokers’ change in salivary aldehyde concentrations pre/post study cigarette(s) administration will be lower in the “conventional” condition than the “natural,” “organic,” and own brand conditions.

Aim 3: Examine if relationships in Aim 1 differ by gender.

H_{3.1}: A greater proportion of women than men will rate the cigarettes in the “natural” and “organic” conditions as having fewer chemicals relative to cigarettes in the “conventional” condition.

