Session 2 is the participant’s own brand assessment. Study personnel will collect a CO reading (to confirm abstinence), assess harm perceptions pre-administration of the product, collect a saliva sample, allow the participant to smoke their cigarettes (ad lib) for 15 minutes (consuming as much as they like) with the topography equipment attached, assess subjective effects, collect a saliva sample and CO reading directly after self-administration, and administer the purchase task. The purpose of this session is to understand how reinforcing participants find their own brand and is useful for disentangling the effect of the exposure from the effect of smoking a novel cigarette. For example, if topography results are null, we can use the OB condition topography data to evaluate to what degree are our results due to participants not liking the experimental cigarette. We will also use data from Session 2 to describe NAS smokers’ OB evaluations and to compare them to non-NAS smokers’ OB evaluations. Collecting expectancies and subjective effects will help us understand the motivations NAS smokers have for using their preferred brand.

Sessions 3-5 are the experimental exposure sessions and will have identical protocols other than the introduction of different advertising exposures. Study personnel will collect a CO reading (to confirm abstinence) and a saliva sample, introduce the cigarette to be used that day (see “Description of the exposure”), assess participants’ expectancies, measure their smoking topography for 15 minutes of ad lib use, collect their subjective impressions of the cigarette, and

collect a second CO reading and saliva sample. During the final session, we will debrief the participant about the study (including clarification that “organic” and “natural” cigarettes are not reduced-harm products) and assess whether participants were deceived by the protocol by asking them to re-state their understanding of the purpose of the study.

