Outcomes. Our primary outcomes are differences by condition in: 1) belief that the cigarette has fewer chemicals (expectancies); 2) chemical aftertaste (subjective effects); 3) total puff volume (topography); and, 4) salivary aldehydes concentration (biomarkers of exposure).

Measures. Table 2 presents a summary of our proposed measures and schedule of assessments. We include descriptions of plans for additional measures described in Table 2 in the appropriate sections below.

At Session 1 we will collect: demographics, tobacco use history and current behavior, the Fagerstrom Test for Nicotine Dependence (FTND), the Ethically-Minded Consumer Behavior Scale (Factor 1), and the Organic Product Scale. We will assess health concern about participants’ own smoking using an item from the Population Assessment of Tobacco and Health (PATH) Study, which was previously associated with NAS preference in our team’s descriptive study of NAS smokers in 2016.²²

Expectancies: We will assess expectancies directly after exposing participants to the experimental condition in Sessions 3-5. Items are rated on a 5-point Likert scale (1 = “definitely untrue”, 5 = “definitely true”) and begin with the statement, “Compared to your own cigarettes that you usually smoke, the cigarettes you will smoke today ...” Expectancy items are listed in Table 2. The primary expectancy outcome measures is whether the experimental cigarette has

fewer chemicals than the participants' usual cigarette; this choice was informed by our pilot study data, which suggested that the perceived presence/absence of chemicals plays a significant role in smokers' understanding of the source of the harm of smoking.³² Data from additional measures in this section will be used to describe participants health risk expectancies connected to their own brand of cigarettes, and to evaluate the validity of these items as a composite score describing the health risk expectancies for natural/organic cigarettes.

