Sample size calculations were performed using GLIMMMPSE Version 3.⁴³ Though a Bayesian model averaging approach will be used, sample size calculations using a non-Bayesian approach are applicable here because they correspond to the model that is believed to be most likely true *a priori*, and also because we plan to use uninformative priors on the parameters in the model, which makes our analyses comparable to the non-Bayesian approach that is used for sample size calculations. As we do not have pilot data to inform our sample size calculations for the NAS/non-NAS group, our sample size calculations are based on the group means by gender that were observed in the pilot study on “total puffs” and a standard deviation of 5.5.³¹ Given NAS smokers’ preexisting misperceptions about natural/organic cigarettes, we anticipate that group means will be more extreme in the NAS/non-NAS group.⁴⁴ Thus, the minimum sample size required for Aim 3 analyses should be sufficient to address the Aim 2 analyses. Assuming an intraclass correlation between repeated measurements of 0.5, 40 total subjects are needed to detect a significant interaction between gender and condition (natural/organic vs conventional/own brand) at 90% power and a significance level of 5%, while 99% power requires 68 subjects. Since these assumptions use information based on only 22 subjects in the pilot study, sample size calculations were also performed with an effect size 50% smaller and a

covariance matrix 50% larger than assumed: under these conditions, 90% power is achieved with 228 total subjects. Fewer subjects are needed to detect differences hypothesized in Aim 1 at each given power; for example, under the smallest effect size observed in the topography pilot data (which assumes a mean difference of 120ml with standard deviation 165ml), 120 subjects are needed to achieve 90% power under an effect size that is 50% smaller and covariance matrix that is 50% larger than assumed. Thus, we will enroll 125 participants per cigarette type (250 total, though we have budgeted for up to 300 participants to account for loss to follow up) to ensure at least 228 participants complete the full study. Our proposed sample size is adequate to detect a similar topography effect size to our pilot study, examine moderation by NAS preference and gender, and allow for adjustments to the significance level due to multiple comparisons.

Statistical analyses

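### The fewer-chemicals item is already relative to the own brand, so the own-brand term subtracted in H2.1 contrasts 3) and 4) is missing, mismatched or redundant, depending on what Session 2 asks

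*Combined protocol and SAP*

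**What the plan says.** Under Measurement instruments and measures, the Expectancies paragraph gives all items a common stem, "Compared to your own cigarettes that you usually smoke, the cigarettes you will smoke today", and defines the primary outcome as whether the experimental cigarette has "fewer chemicals than the participants' usual cigarette". On timing it says: "We will assess expectancies directly after exposing participants to the experimental condition in Sessions 3-5".

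Study procedures is less clear about Session 2, the own-brand visit. Staff are to "assess harm perceptions pre-administration of the product", and the stated purpose includes "Collecting expectancies and subjective effects will help us understand the motivations NAS smokers have for using their preferred brand". The section also says "We will also use data from Session 2 to describe NAS smokers" in terms of their own-brand evaluations and to compare these with those of non-NAS smokers. No item or stem is given. Measures refers to Table 2 for items and schedule; that table is not in the text available here, and its absence is not held against the plan.

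H2.1 (Aims & Hypotheses) expects more NAS than non-NAS smokers to rate natural and organic as lower in chemicals relative to conventional, "but not relative to their own brand condition". Hypothesis testing numbers eight effects for H2.1 and H2.2 together. I write them E1 to E8: own brand, conventional, natural and organic for NAS smokers (E1-E4), then the same for non-NAS smokers (E5-E8). Contrast 3) compares E4 - E1 with E8 - E5, and contrast 4) compares E3 - E1 with E7 - E5. An interval that contains 0 is to be read as evidence for the null, which is the result predicted for both contrasts.

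**The concern.** H2.1 and H2.2 share one set of contrasts. For H2.2 this is coherent: the aftertaste scale has absolute anchors, so an own-brand comparison needs an own-brand rating to subtract. The fewer-chemicals item differs, because the participant has already made that comparison when answering. Subtracting E1 and E5 then removes the own brand a second time, and what is removed depends on a Session 2 measurement that the text leaves open.

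At stake is the own-brand clause of H2.1. Depending on Session 2, contrasts 3) and 4) may have no data behind E1 and E5, may reject when the two groups gave identical organic or natural answers, or may be needlessly imprecise. Because an interval containing 0 counts as the predicted result, imprecision works in favour of the hypothesis.

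**Working it through.** **Inputs.** From the documents: the item stem, the definitions of contrasts 3) and 4), the logit link for this outcome, uninformative priors in the main analysis, and 228 completers (Sample size calculations), taken as 228/2 = 114 per brand group. The documents give no response rates, so all rates below are assumptions. There is no figure of the plan's own to reproduce on this point.

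**Identity, on any scale.** Contrast 3) = (E4 - E1) - (E8 - E5) = (E4 - E8) - (E1 - E5). The direct own-brand-relative comparison is E4 - E8, so contrast 3) departs from it by -(E1 - E5). Contrast 4) is the same with E3 and E7.

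**Item not asked in Session 2.** E1 and E5 have no data, so contrasts 3) and 4) cannot be estimated.

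**Asked with a different stem** (for example, an absolute rating of the own brand). E1 - E5 is then a difference on another question.
- Take the proportion scale, with organic 'true' 50% in both groups (so E4 - E8 = 0) and own-brand 'true' 30% NAS v 10% non-NAS.
- Shift = -(0.30 - 0.10) = -0.20.
- SE, treating answers as independent = sqrt[(0.25 + 0.21 + 0.25 + 0.09)/114] = sqrt(0.80/114) = 0.0838.
- P(95% interval excludes 0) = Phi(0.20/0.0838 - 1.96), about 0.67.
- With organic rates of 30-50%, non-NAS own brand at 10% and within-person correlation 0 to 0.3, the probability is 23-34%, 67-85% and 94-99% for own-brand gaps of 10, 20 and 30 points.

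**Asked with the same stem.** The own brand is rated against itself. If E1 = E5, contrast 3) equals E4 - E8 exactly: the target is right and the subtraction is redundant. The cost depends on the scale. At 50% organic in both groups:
- Logit scale, direct: SE = sqrt[2/(114 x 0.25)] = 0.265.
- Logit scale, contrast 3), group-specific own-brand effects, own-brand 'true' 5%: SE = sqrt[2/(114 x 0.25) + 2/(114 x 0.0475)] = 0.66. At 2%: sqrt[2/(114 x 0.25) + 2/(114 x 0.0196)] = 0.98.
- At 2%, P(no 'true' answer in one group) = 0.98^114 = 0.10, so P(at least one empty group) = 1 - 0.90^2 = 0.19. At 1% the figures are 0.32 and 0.54. With an empty group, the logit effect is not identified under an uninformative prior.
- Proportion scale: half-width 1.96 x sqrt(0.50/114) = 0.130 directly, and 1.96 x sqrt[(0.50 + 2 x 0.0196)/114] = 0.135 for contrast 3) at 2%. The difference is immaterial.
- A single own-brand effect shared by both groups, which Statistical analyses allows, sets E1 = E5 and cancels.

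**Precision of the direct test.** At 50% 'true', the half-width of E4 - E8 is 0.130 and its SE 0.0662. With a true difference of 0, a 20-point margin is met with probability 2 x Phi[(0.20 - 0.130)/0.0662] - 1 = 0.71, and a 25-point margin with 0.93.

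**The case against.** A reader might infer that contrasts 3) and 4) fail whatever Session 2 asks. The documents do not support that. With the same stem and equal own-brand effects, contrast 3) is the very quantity recommended below, and on the proportion scale or with a common own-brand effect almost nothing is lost. The plan uses a logit link but describes these contrasts as differences in mean outcomes, so the scale on which harm would arise is not fixed. This part of the objection stands.

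A reader might also take the Sample size section, which cites NAS smokers' "preexisting misperceptions about natural/organic cigarettes, we anticipate that group means will be more extreme in the NAS/non-NAS group", as a statement that own-brand answers will differ between groups. That sentence justifies reusing a calculation based on puffs by gender; it says nothing about own-brand expectancy ratings. The 10, 20 and 30-point gaps are therefore pure assumption.

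Nor can one conclude that imprecision will usually deliver the predicted null. That needs the same stem, the logit scale, group-specific own-brand effects, very few own-brand 'true' answers and no pooling. Hypothesis testing commits to multilevel pooling within each aim, which would reduce the problem.

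Finally, it is no extra fault of the subtraction that, when E1 = E5, H2.1's pattern requires equal organic answers in the two groups, with the difference lying in the conventional answers. That follows from the hypothesis and the item, and applies equally to the direct test.

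The objection does not remove the main difficulty. The Session 2 and Expectancies texts do not agree, and under no reading do contrasts 3) and 4) target the clause better than the direct comparison.

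**Conclusion.** The point holds in a limited form. As written, the own-brand term in contrasts 3) and 4) for H2.1 is without data, on a different reference frame, or redundant. Which applies cannot be settled from the text, and Table 2 may answer it. The size is conditional: about 67% false exclusion of 0 in the different-stem example; an SE of 0.66 to 0.98 against 0.265 with the same stem on the logit scale; little harm on the proportion scale. These figures rest on assumed rates and 114 per group; the SE comparison also assumes independent answers and no pooling.

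Separately, following the rule that an interval containing 0 shows no difference could give a wrong conclusion: even the direct contrast has a half-width of 13 points at 50% 'true'.

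Only the own-brand limb of H2.1, a secondary hypothesis, is affected. H1.1, contrasts 1) and 2), and H2.2 are untouched by the item wording.

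**What to change.** 1. Reconcile Study procedures (Session 2) with the Expectancies paragraph: state which expectancy item and stem, if any, is used at the own-brand visit.
2. For H2.1 only, replace contrasts 3) and 4) with E4 - E8 and E3 - E7, estimated from Sessions 3-5. These are available under every reading. Use any Session 2 expectancy item to describe own-brand evaluations, as Study procedures intends.
3. Name the scale (logit or proportion). Report the share answering 'true' by NAS status with 95% credible intervals, noting that each group's yardstick is its own brand.
4. Do not read an interval that contains 0 as evidence of no difference. Fix in advance a margin or a Bayes-factor criterion; the plan already uses Bayes factors for model choice. Apply the same rule to contrasts 3) and 4) where they stay for H2.2.

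The cost is SAP wording, with no new data. The downside is a narrower, largely descriptive own-brand limb: at 50% 'true', a margin of 13 points or less cannot be met, and with a true difference of 0 a 20-point margin is met in about 71% of trials and a 25-point margin in about 93%.

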The overall purpose of this study is to examine the relationship between the “organic” and “natural” descriptors and health risk expectancies, subjective effects, topography, and resulting chemical exposures. This is a within-person human laboratory study with assessments of psychological, behavioral, and biological exposure data. The procedures described here were tested in a pilot study conducted in late 2019.³² Data will be collected at the University of Nevada, Reno (Reno, Nevada, USA), the Desert Research Institute (Reno, Nevada, USA), and the University of Pennsylvania (Philadelphia, Pennsylvania, USA). The study will consist of 5 total lab visits: the baseline visit, and four experimental visits (own brand comparator condition, “natural” advertising condition, “organic” advertising condition, and “conventional” advertising condition) (Figure 1). Conditions will be randomized and counterbalanced to account for order effects.

This is a deception study; participants will believe that they are participating in market testing cigarettes and will not know the real purpose of the study. We created a faux tobacco brand and associated cigarette mailer for the organic, natural, and conventional cigarette varieties (Figure 2). While participants will believe they are testing three varieties of a new brand of cigarette, in reality they will use the same product (Nat’s “Rich Smooth Taste” cigarettes, the blinded experimental cigarette) three times. None of the labs involved in data collection are in medical or public health-focused buildings, which aids in the study deception. Results from our pilot study demonstrate that this study design will deceive participants.³² At the last pilot study visit, we asked our 22 pilot study participants to restate the purpose of the study as they saw it. Though a handful of participants inferred that things weren’t *exactly* as they seemed, none of the participants described the actual study purpose. We will include the same question at the end of Session 5 to identify participants who were not deceived by the study (see Missing Data).

Aims & Hypotheses

Aim 1 hypotheses are primary; Aims 2 and 3 hypotheses are secondary. The specific aims and associated hypotheses are:

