Subjective ratings: We will assess subjective ratings after each ad lib session using items developed by the tobacco industry and the UPenn laboratory and adapted given pilot study results.³¹ Subjective rating items are listed in Table 2. The "chemical aftertaste," "clean tobacco taste," and "overall feeling" items are new items that reflect how smokers discussed the subjective effects of smoking an organic cigarette in our pilot study³¹; the "chemical aftertaste" is the main outcome for the subjective ratings. Items are rated on a 100 mm visual analog scale with item-specific anchors (e.g., strength: 0 = "no chemical aftertaste," 100 = "strong chemical aftertaste"). As with the additional expectancies items, the additional subjective effects items will be used to characterize participants' subjective effects from their own brand cigarettes (comparing NAS and non-NAS smokers will be especially informative), and to evaluate the validity of these items as a composite score describing subjective effects of natural/organic cigarette smoking.

As exploratory behavioral measures, we will also include a cigarette purchase task (CPT), a behavioral economic measure, to assess demand in each cigarette condition. The CPT will ask participants how many of the cigarette types (e.g., natural vs organic vs own vs conventional) they would be willing to consume a day at escalating price points (i.e., starting at free then increasing by 5 cent increments (i.e., \$1.00 per pack) to \$1.45 per cigarette or \$29 per pack). These responses are used to calculate five demand indices: breakpoint (the first price that consumption is suppressed to zero), Omax (the maximum expenditure for the product), intensity (consumption at the lowest price, i.e., zero), Pmax (price at Omax), and elasticity (sensitivity to change in price); the first four are observed while the last is computed based on a combination of these items. Breakpoint will be the primary CPT-related outcome for these exploratory analyses. In addition to capturing actual smoking behavior with the topography device, assessing both behavioral intentions and demand indices obtained by the CPT will provide us with multiple behavioral measures to comprehensively understand how organic/natural expectancies influence behavior.

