H(1.1), H(2.1), H(3.1): Expectancies (Have fewer chemicals)

We will create a binary variable from a 5-point Likert scale (Definitely true, Somewhat true, Neither true nor false, Probably false, Definitely false) for this measurement to indicate if the participant believes the cigarettes smoked during the visit have fewer chemicals (if answered Definitely true or Somewhat true) or not (if answered Neither true nor false, Probably false, or Definitely false). We will use an approach that models the probability of belief that cigarettes smoked during the visit have fewer chemicals, and we will use the logit link function so that the form of the best model will resemble a mixed effects logistic regression model; other link functions (e.g. probit) will be considered if model fit is a concern.

H(1.2), H(2.2), H(3.2): Subjective effects (chemical aftertaste)

Chemical aftertaste will be used as the outcome, which will have items rated on a 100 mm visual analog scale with item-specific anchors (e.g., strength: 0 = "strong chemical aftertaste," 100 = "no chemical aftertaste"). We do not anticipate many measurements on the boundaries (0 or 100), which makes Normality an appropriate assumption for the residuals. However, if there are many measurements on the boundaries (i.e. if Normality does not seem like an appropriate assumption for the residuals), then a binary outcome that indicates if the measurement is greater than 50 will be used instead, and we will use the logit link function so that the form of the best model will resemble a mixed effects logistic regression model (like above for the expectancies outcome); other link functions (e.g. probit) will be considered if model fit is a concern.

H(1.3), H(2.3), H(3.3): Topography (total puff volume)

Normality is expected to be an appropriate assumption for total puff volume (a quantitative variable) based on pilot data.³² However, if Normality does not seem like an appropriate assumption for the residuals in this sample, then a transformed outcome (e.g. log-transformation) will be considered (particularly if the outcome is skewed). If normality is still violated, we will consider a binary outcome using a median cutoff and use the logit link function so that the form of the best model will resemble a mixed effects logistic regression model (like above for the expectancies outcome); other link functions (e.g. probit) will be considered if model fit is a concern.

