H(1.4), H(2.4), H(3.4): Biomarkers of exposure (Salivary aldehydes)

Concentrations of formaldehyde and acetaldehyde will be used as the outcome (difference between pre- and post-visit), where Normality is expected to be an appropriate assumption for the error term. However, just as with the other outcomes, if Normality does not

seem like an appropriate assumption, a transformed outcome (e.g. log-transformation) will first be explored, and if normality still does not hold, then we will consider a binary outcome using a median cutoff and use the logit link function so that the form of the best model will resemble a mixed effects logistic regression model (like above for the expectancies outcome); other link functions (e.g. probit) will be considered if model fit is a concern.

Hypothesis testing

H(1.1 - 1.4) are primary, and under the null hypotheses in H(1.1 - 1.4), the natural and organic condition means are equal to the conventional condition means. To test the hypotheses in Aim 1, we will first determine if the effects of the condition depend on gender and NAS-smoking status (as hypothesized in H(2.1) - H(3.4)). If the effect of the condition does not depend on gender or NAS-smoking status, then we will estimate the following effects in our model:

1. effect of the conventional condition
2. effect of the natural condition
3. effect of the organic condition

The null hypotheses in H(1.1 - 1.4) state that the conventional condition is equivalent to the natural and organic conditions. We can therefore test H(1.1 - 1.4) by estimating 95% credible intervals for the difference between the effects of the organic and natural conditions and the conventional condition. This will yield two credible intervals (one for the difference between natural and conventional effects, and another for the difference between organic and conventional effects) for each outcome (four outcomes) therefore making 8 total credible intervals of interest in Aim 1. If the effects of the condition depend on NAS-smoking status but do not depend on gender, then we will estimate the following effects in our model:

1. effect of the own brand condition for Non-NAS smokers
2. effect of the conventional condition for Non-NAS smokers
3. effect of the natural condition for Non-NAS smokers
4. effect of the organic condition for Non-NAS smokers
5. effect of the own brand condition for NAS smokers
6. effect of the conventional condition for NAS smokers

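### The chemical aftertaste scale, a primary outcome, is anchored in opposite directions in the measures and analysis sections, so H1.2, H2.2 and H3.2 can be concluded with the sign reversed

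*Combined protocol and SAP*

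**What the plan says.** Chemical aftertaste is a primary outcome. The Subjective ratings paragraph says "the 'chemical aftertaste' is the main outcome for the subjective ratings", and Aims & Hypotheses states "Aim 1 hypotheses are primary; Aims 2 and 3 hypotheses are secondary", which makes H1.2 primary and H2.2 and H3.2 secondary.

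The direction of the scale is given in three places:

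- **Measurement instruments and measures, Subjective ratings:** "0 = 'no chemical aftertaste,' 100 = 'strong chemical aftertaste". Higher means more chemical aftertaste.
- **Statistical analyses, subsection for H(1.2), H(2.2), H(3.2):** "0 = 'strong chemical aftertaste,' 100 = 'no chemical aftertaste". Higher means less chemical aftertaste.
- **Aims & Hypotheses, H1.2 (H2.2 and H3.2 use the same phrase):** ratings in the natural and organic "conditions will be higher (e.g., closer towards the “less chemical aftertaste” side of the scale". Higher means less chemical aftertaste.

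The analysis subsection adds a fallback if many ratings lie at the ends of the scale: "a binary outcome that indicates if the measurement is greater than 50 will be used instead". Under Hypothesis testing, Aim 1 is tested by "estimating 95% credible intervals for the difference between the effects of the organic and natural conditions and the conventional condition".

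**The concern.** The two sets of anchors are exact mirror images, and nothing in the text converts one to the other. The hypotheses fit the analysis section, but the measures section is the one that describes how the data are collected. An analyst who receives ratings recorded as the measures section describes, and follows the analysis section literally, would read a fall in chemical aftertaste as a rise.

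Direction is the substance of H1.2: do the descriptors make the same cigarette seem less chemical? The introduction says the results may guide regulatory decisions on cigarette marketing, so a reversed finding would be consequential. The Subjective ratings paragraph also describes chemical aftertaste as a new item, so the documents point to no established scoring convention. The same paragraph plans to evaluate a composite of the subjective items, which also requires each item's direction to be known.

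**Working it through.** The plan gives no numerical figure for this outcome, so the check compares the texts and follows the reversal through the planned contrasts.

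**1. Consistency of the texts.** Let R be a rating on the measures-section anchors (100 = strong) and A a rating on the analysis-section anchors (100 = none). The same experience gives A = 100 − R. H1.2, H2.2 and H3.2 predict higher A, which is lower R. As worded, they are right on the analysis-section scale and backwards on the measures-section scale.

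**2. Effect on the contrasts.** With N = natural (or organic) and C = conventional:

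- Aim 1: A_N − A_C = (100 − R_N) − (100 − R_C) = −(R_N − R_C).
- Aims 2 and 3: the difference of two such differences between subgroups also changes sign exactly.
- With the planned uninformative priors, an interval (L, U) becomes (−U, −L). It has the same width and contains 0 in exactly the same cases.
- Fallback: A > 50 is the same event as R < 50. Apart from ratings of exactly 50, the indicator becomes its complement.

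**3. Would the test rules detect a reversal?** Aim 1 takes equality as the null and examines the interval for the difference. The rules for H2.2 and H3.2 ask only whether the interval contains 0. The one remark requiring the difference to lie in the hypothesised direction is attached to H3.3 and H3.4. A reversed score therefore passes the rules written for H1.2, H2.2 and H3.2.

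**4. How much of the plan is touched.** There are 3 aims × 4 outcomes = 12 hypotheses, of which 3 concern aftertaste. The plan's Aim 1 interval counts reproduce as follows:

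| Condition effect depends on | Intervals per outcome | Total over 4 outcomes | Aftertaste |
|---|---|---|---|
| neither moderator | 2 | 8 | 2 |
| one moderator | 4 | 16 | 4 |
| both moderators | 8 | 32 | 8 |

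The share is one quarter in each branch.

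**5. Numerical illustration (assumed inputs).** Only n = 228, the plan's target for completers, comes from the document. Assumed on the analysis-section scale: means of 50 (conventional) and 60 (natural), person SD 15 and residual SD 17, which gives a per-condition SD of √(15² + 17²) = √514 ≈ 22.7, with ratings truncated to 0–100. For the gender contrast, women were given a further shift of 5. One simulated data set was scored both ways, with mean ± 1.96 standard errors standing in for the credible interval:

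| Quantity | Analysis-section anchors | Measures-section anchors |
|---|---|---|
| natural − conventional | +10.4 (7.5 to 13.4) | −10.4 (−13.4 to −7.5) |
| rating > 50, natural vs conventional | 66% vs 44% | 34% vs 56% |
| women − men in that difference | +6.3 | −6.3 |

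The sizes depend on the assumptions; the sign change does not.

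**The case against.** The strongest reply is that the intended direction is recoverable. All three hypotheses and the analysis section agree that higher means less aftertaste, and the hypotheses say so in words. The measures section is the lone outlier and may be a transposed example: both anchor statements are introduced as examples and carry the label strength, which does not match anchors that name chemical aftertaste. Table 2, which lists the items, is not in the text available here and may show the administered anchors. Harm also needs two events that the document does not establish: the scale was administered as the measures section says, and no one recoded it.

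Several limits stand:

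- Reversal does not change whether the interval excludes 0, so detection, power and error rates on the continuous outcome are unaffected.
- The part of H2.2 that predicts no difference relative to own brand is unaffected.
- H2.2 and H3.2 are secondary.
- The fallback at 50 is not expected to be used, since the plan anticipates few ratings at the ends of the scale.

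These points limit the size of the problem without removing it. Agreement between the hypotheses and the analysis section shows what the authors meant to analyse, not what the software stored. The shared strength label appears in both places, so it cannot explain why the anchors differ. Table 2 could show which statement is right, but the two sections would still conflict.

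**Conclusion.** The concern holds and must be fixed. As written, the plan defines a primary outcome in two opposite directions with no reverse-scoring step. If ratings are collected as the measures section states and analysed as the analysis section states, the direction of H1.2 and H3.2, and of the conventional-condition part of H2.2, is fully reversed, as is the meaning of the fallback indicator.

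The reach is one of four primary outcomes and one quarter of the Aim 1 intervals. The consequence is conditional on that combination of collection and analysis, and the error would lie in the direction reported, not in whether a difference is found. The sign change is exact algebra and rests on no assumption about effect size; only the illustrative magnitudes do.

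**What to change.** 1. Establish from the survey programming and export coding which orientation was shown and stored, and confirm that it is the same at every collecting laboratory. Do not infer it from the direction of the observed condition differences, because that would let the result choose its own sign.
2. State that raw orientation identically in the Subjective ratings paragraph and in the analysis subsection, and make sure Table 2 agrees.
3. Define a separately named analysis score on which higher means less aftertaste. If the raw scale already runs that way, it is the raw score. If the raw scale has 100 = strong, it is 100 minus raw, computed before any model is run.
4. Define the above-50 fallback on the analysis score, and tie the wording of H1.2, H2.2 and H3.2 to that score.
5. Add to the test rules for the directional comparisons in these three hypotheses that support requires the interval to exclude 0 in the hypothesised direction.

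The cost is a few sentences in the plan and one check of the survey coding. Design, sample size and model are unchanged, and there is no statistical downside.
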